1. Discomfort during the procedure: To minimize discomfort, participants will sit at the edge of the bed with supports and pillows to keep them in an ergonomic position. Lidocaine will be used for local anesthesia. Only physicians experienced in performing lumbar catheters will perform this procedure.
2. Back soreness: Participants are provided with information sheets on using heat, stretching, and acetaminophen if back soreness occurs.
3. Feeling faint: If a participant feels faint, s/he will be assisted in lying down in the bed until the feeling has passed. The lumbar catheter can be performed with participants lying down on their side, in this case.
4. Post-lumbar catheter headache: This risk will be minimized by having the participants lie in bed with their heads down (the Trendelenburg position) for one hour after the catheter is removed. Participants will remain in bed for 6-8 hours after the catheter is removed. Participants are also informed they can minimize this risk by having caffeine after the lumbar catheter is removed, and drinking plenty of water throughout the study while the catheter is in place. If a post-lumbar catheter headache does occur, participants will be offered treatment with a “blood patch.”
5. Bleeding: Individuals with this risk (blood clotting problems or taking anticoagulants) are excluded from participation in the study.
6. Infection: Proper sterile technique will be used during all lumbar catheter placements. At the end of the study immediately prior to the removal of the catheter, an additional 2 ml of CSF will be drawn, when available, and sent to the lab to check for any signs of infection. Further, participants are given a 24/7 phone number for a member of the research team after discharge from the Clinical Research Unit in case of complications.

Intravenous catheter

1. Discomfort during the procedure: Only physicians and nurses experienced in placing intravenous catheters will perform the procedure.
2. Bruising at phlebotomy site: Discomfort from bruising can be alleviated by moist heat pack, which can be provided in the Clinical Research Unit.
3. Feeling faint: If a participant feels faint, s/he will be assisted in lying down in the bed until the feeling has passed. Participants will be encouraged to drink plenty of water during the study, to minimize the chance of feeling faint.

Suvorexant

1. Somnolence and confusion: Participants will be on the Clinical Research Unit throughout the study with 24-hour nursing coverage. Participants will only take suvorexant in this monitored setting. Nurses will be available to assist all participants if they wake up confused and somnolent during the night. Further, the participants will be under constant video

monitoring while in the Clinical Research Unit; this video is not recorded and is only viewable by the nursing staff. Somnolence may be severe in participants with compromised respiratory function; therefore, obstructive sleep apnea and chronic obstructive pulmonary disease are exclusion criteria. Suvorexant will be discontinued if somnolence and/or confusion is distressing to the participant or severe.

2. Next day drowsiness: Participants will be monitored in the Clinical Research Unit prior to discharge and will be assessed for level of alertness with a Stanford Sleepiness Scale and psychomotor vigilance testing performed upon admission and at the time of discharge. The principal investigator will evaluate the participant and review these measures prior to approving discharge.
3. Additional mild and common reactions to suvorexant include headache, dizziness, abnormal dreams, diarrhea, dry mouth, and cough: Participants will be on the Clinical Research Unit throughout the study with 24-hour nursing coverage. Participants will only take suvorexant in this monitored setting. Nurses will be available to assist all participants if they develop these symptoms. Suvorexant will be discontinued if reactions are distressing to the participant or severe.
4. Abnormal sleep behaviors: All participants will take suvorexant on the Clinical Research Unit at Washington University which has 24 hours a day nursing coverage monitoring the participants. Participants will only take suvorexant in this monitored setting. Nurses will be available to assist all participants if they develop these symptoms. Further, the participants will be under constant video monitoring while in the Clinical Research Unit; this video is not recorded and is only viewable by the nursing staff. Suvorexant will be discontinued if reactions are distressing to the participant or severe.
5. Suvorexant may interact with multiple medications: Participants taking medications that interact with suvorexant will be evaluated by the principal investigator. If the potentially interacting medications cannot be discontinued, then the participants will be excluded from the study.
6. Depressed mood and/or suicidal ideations: All participants will be screened for suicidal ideations and psychiatric disorders. All participants with psychiatric disease requiring medications will be excluded both to control this risk and also because psychiatric medications may interfere with sleep. Participants with suicidal ideations will be excluded. This risk is also controlled because participants will only take suvorexant for 2 nights in the monitored setting of the CRU with 24 hours a day nursing coverage.

Actigraphy

1. Irritation of skin from strap of actigraph: Participants will be permitted to wear the actigraph over long sleeves or a wrist band, or they can remove the actigraph at any time.

Polysomnogram (Sleep study)

1. Irritation of skin from electrodes used during study: When possible, an alternative cleaning agent or adhesive will be used. If irritation is more than mild, that electrode will not be used for the study.
2. Worse sleep quality: Participants will be allowed to nap until 17:00 before going home after the conclusion of the study.

Privacy/confidentiality

1. Breach of privacy/confidentiality:
 - All data will be labeled with a random number rather than with any identifiable information. All physical materials (such as paper, data storage disks, and biospecimens) will be stored in locked cabinets/freezers in a locked research area, accessible only to the research team. All electronic information will require a password and will be accessible

- only to the research team. Any paper or electronic information that could link a participant to the study (such as consent documents) will be stored separately from all other study materials, also in a secure manner that is accessible only to the research team. If a report or article is written about this study or the study data are shared with other researchers, it will be done in such a way that participants cannot be identified.
- For individuals who give verbal consent for the Phone screen, and then do not “pass” the screening questions, their phone screen will be shredded, and *no* information is kept about them.

Protections for research involving vulnerable populations: This project does not involve vulnerable populations.

Plan for adverse events: Response to an adverse event or risk will differ based on the type and severity of the event. A Data Safety Monitoring Committee (DSMC) will serve to mitigate these risks and ensure a formal process for dealing with adverse events.

- *Data Safety Monitoring Committee:* A DSMC consisting of experts in the study procedures and the effects of sleep disorders on cardiac and psychiatric morbidities has been established for the proposed study.
 - Qualified individuals monitoring the study: The DSMC members have substantial experience and expertise in this area of research and in clinical research, and are qualified to monitor the study.
 - The DSMC will meet prior to enrollment of any participants, to review study procedures and potential adverse events, and then provide guidance on HRPO application and consent/informational materials.
- *Web-Based Instruction on Conducting Human Research:* In accordance with the NIH policy effective October 1, 2000, this is to certify that Washington University key personnel involved in the design and conduct of the human subjects research aspect of this proposal have been educated on the protection of human research participants. An interactive web-based program that provides information on conducting human research and the informed consent process is organized into five modules. These modules include detailed information, examples and exercises related to basic principles, history, consent form process, and after approval requirements such as continuing review and adverse events.
- *Review of adverse events:* All personnel who will be in contact with participants and/or data are prepared to identify adverse events and have been instructed to report their occurrence immediately to the principal investigator.
- *Definition:* An adverse event will be defined as any negative change in health related to study-related procedures.
- *Classification of Events:* A Safety Documentation form will assess for details of any adverse events, severity, and relatedness to study procedures.
- *Data Collection Procedures for Adverse Events:* At each visit and with each interaction/phone call, adverse events will be screened for and recorded. If any adverse events have occurred, these will be logged in the Safety Documentation form.
- *Reporting Procedures:* The Safety Documentation form will be discussed during the DSMC meetings. The DSMC will meet according to participant completion goals (after 15, 23, 30, 38, and 45 participants complete the study). If a serious adverse event occurs, the DSMC will meet as soon as possible to determine the course of action. If the DSMC deems changes to the study are necessary for safety reasons, the study will halt immediately until the changes have been approved through the Washington University HRPO.

- *Criteria for stopping the study:* Circumstances that would warrant stopping the study are not anticipated. However, should any circumstances arise that compromise the safety of the participants, they will be reported to the DSMC who will suspend research until appropriate safeguards allow continuation of the study.
- *Adverse Event Reporting Period:* There will not be a set end-date for reporting adverse events.
 - Expected adverse events (*i.e.* are listed above and on consent forms) will be discussed at DSMC meetings. Also, they will be reported to the HRPO during annual renewals.
 - Unexpected serious adverse events will be reported within 10 days, per HRPO requirements.

The only anticipated adverse events that would require medical intervention are:

1. A post-lumbar catheter headache that does not resolve with conservative measures such as rest, hydration, and caffeine intake. This will be treated with “blood patch” in the Clinical Research Unit, at no cost to the participant.
2. Side effects to suvorexant such as somnolence and confusion upon waking. Risks from suvorexant are minimized with the inclusion/exclusion criteria and that participants will only receive the drug for 2 nights in the monitored setting of the Clinical Research Unit at Washington University. If any severe adverse events occur on suvorexant, then the drug will be discontinued and the participant monitored closely.

3. Potential Benefits of the Proposed Research to Human Subjects and Others

Potential benefits to participants

The only direct benefit to the participant is that they will be screened for sleep apnea with the STOP-Bang questionnaire and other sleep disorders by the history and examination of the principal investigator. This may result in a diagnosis that may have been made later. Participants who screen fail due to concerns for a sleep disorder like sleep apnea will be informed of the reason for exclusion, withdrawn from the study, and encouraged to follow-up with their primary care physician.

Potential benefits to others

Potential benefits to society will be knowledge of whether or not sleep modification can change CSF A β production and concentrations. If CSF A β production and concentrations can be modified by improving sleep efficiency, then this opens up a new potential treatment option for the prevention or treatment of Alzheimer's disease from which they, or future AD patients, may benefit.

Risks vs. benefits: The benefit of the knowledge to be gained in the study, as well as the personal benefit to participants, outweighs the risks in the study. Risks have been minimized to the greatest possible extent, while still achieving the scientific aims of the research study.

4. Importance of the Knowledge to be Gained

The knowledge to be gained in this study is very important because it is the first study directly assessing the relationship of poor sleep efficiency and A β in a relevant human population. If this study is successful, it will lead to treatments targeting sleep for possibly delaying or reducing risk of AD. AD is a devastating neurodegenerative disorder characterized by progressive cognitive decline. The public health impact of dementia is enormous with the number of individuals with

AD projected to increase from 5 million Americans in 2010 to 13.5 million Americans in 2050. Even a modest reduction in the risk of AD would have a tremendous public health impact. Demonstrating that sleep alters A β may suggest innovative AD treatment approaches that involve sleep therapies.

5. Data and Safety Monitoring Plan

This study is a clinical trial, however it is not an NIH-defined phase III clinical trial. Suvorexant is already FDA-approved for the treatment of insomnia. This study will use suvorexant under the FDA-approved indication. Comparisons are being made between poorly-sleeping treated (suvorexant) and untreated individuals (placebo). There is a Data Safety Monitoring Committee and monitoring plan as described in section “*2.B Protections Against Risk*” above. [name]., [name]., [name]., and [name]. will monitor the study for adverse events, adherence to the protocol, inclusion/exclusion criteria, and accrual/withdrawal rates. All serious adverse events will be reported to the Washington University HRPO: a) death – immediately; b) life threatening with 7 calendar days; c) all other SAEs within 15 calendar days using the HRPO Reportable Event Form (SAE report). Should there be an adverse event that occurs that increases the risks to the participants, the following steps will be taken: suspension of the study until risks are re-evaluated and discussed with the HRPO. Other reports that will be generated are yearly summary reports. These will be sent to the HRPO annually.

Given that the study requires significant involvement from the participants, we have taken steps to make the study less taxing for participants. These steps include having nurses available in the CRU for assisting the research participants at all times and providing 24 hour/7 day/week access to study staff and physicians.

All participants will be identified by a deidentified study number to protect patient confidentiality. Participants may be linked to the “sleep quality” study in Epic if they already have a record in the Epic system. Spreadsheets listing the participants’ name and corresponding study number will be managed by the study coordinator, and will be stored in a password protected file behind the Neurology firewall. Only the research team will have access to this spreadsheet. Data monitoring and analysis will be performed by the principle investigator. Data will also be collected on any adverse events related to the study procedures.

All data is electronically uploaded and locked in the [name] laboratory’s database (Firebird 2.1.4) blinded to clinical status and other variables. In collaboration with [name], an expert in modeling at Washington University, the A β stable isotope labeling kinetics (SILK) data will be analyzed with the compartmental model using the SAAM II modeling program blinded to clinical status and other variables. All statistical analyses will be conducted in collaboration with [name], an expert in statistics at Washington University. All data is compared in a pre-specified fashion. All data and results will be available to other investigators upon request.

6. ClinicalTrials.gov Requirements

This study will be registered at ClinicalTrials.gov and the final study results will be reported on the website within 12 months of study completion. This will enable registration of primary and secondary aims and allow for broadest publication in journals.

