45 participants will be randomized to receive a placebo, 10 mg of suvorexant, 20 mg of suvorexant during the CRU stay. Suvorexant is a dual orexin receptor antagonist that is approved by the Food and Drug Administration (FDA) for the treatment of insomnia. Suvorexant is also a drug with the same mechanism of action as was used in experiments to decrease A β with sleep in mice (8), therefore this will be a direct translation of this finding. Further, genetic manipulation of the orexin system to alter the sleep-wake cycle has been shown to drive A β pathology (51).

FDA-approved doses of suvorexant range from 5-20 mg. The drug's mechanism of action is to block orexin-A and orexin-B receptors. The orexin neuropeptide acts in the brain to promote wakefulness. Through antagonism of this system, sleep is induced. In a phase IIb randomized, double-blind, placebo-controlled study of patients with primary insomnia, suvorexant 10 mg increased sleep efficiency from 65.1% at baseline to 82.9% at night 1 and 84.4% at one month (48). Placebo-treated subjects increased sleep efficiency from 65.9% at baseline to 76.8% at night 1 and 77.8% at one month.

Participants will be allowed to sleep as they are able immediately with the lights turned off after medication dispensation (placebo or suvorexant). Nursing staff will use dim red lights (safelights) when collecting CSF and blood in the dark. The lumbar catheter ports will be placed on the outside of the gown sleeve for easy access to minimize disturbance during fluid collection. Participants will then sleep until final awakening the morning. During Day 2, all participants will be in well-lit rooms with regular monitoring for

staying awake and naps will not be permitted. On Day 2 ($t=24$), all participants will follow the same sleep routine except that there will be no infusion of labeled $^{13}\text{C}_6$ -leucine. Participants will receive the same placebo or suvorexant dose as the previous night (Figure 5). The IVs and lumbar catheters will be removed following the last CSF collection ($t=36$). Afterwards, participants will be monitored at the Clinical Research until discharge at approximately 17:00. A β kinetics will be quantified by MS.

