Statistical Analysis and Power Calculation: All participants will be screened to determine if they have good or poor sleep efficiency as described above. 15 participants with good sleep efficiency will be treated with placebo (Aim 1). 45 participants with poor sleep efficiency will be randomized to either placebo (N=15) (Aim 1) or suvorexant 10 mg (N=15) or suvorexant 20 mg (N=15) (Aim 2). Change in CNS A β 40 and A β 42 production, clearance, and concentration in placebo-treated participants with poor sleep efficiency will be compared to placebo-treated participants with good sleep efficiency (Aim 1) and individuals with poor sleep efficiency treated with suvorexant (Aim 2) using a repeated measures analysis of variance (RM ANOVA), or repeated measures analysis of covariance (RM ANOCOVA) when covariates such as age are included in the analysis (49). Correction for multiple comparisons will be performed. A main question is whether the production rate of CSF A β during the production phase differs between subjects with good or poor sleep efficiency, or treated with drug, that will be statistically tested by appropriate interactions between subjects groups and time in the RM ANOCOVA. The average concentration of CSF A β over the entire time course during the sleep period will be tested by the main effects of subjects' groups, adjusting for the possible effects of age. Other parametric mixed effects models incorporating the typical sinusoidal profile over time will also be considered in the analyses. These analyses will be implemented by PROC MIXED/SAS or SPSS (50).

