To determine the sample size, I performed an *a priori* calculation with two-tailed t-tests to detect a difference between two independent means (two groups) for the number of subjects needed to find a difference in the AUC for both A β 40 and A β 42 during the 10-hour sleep period. With the preliminary data for control (good and poor sleep efficiency) and all sleep-induced participants, the mean and standard deviation of A β 40 and A β 42 AUCs (pM*hr) during the 10-hour period from 23:00-09:00 were used for the power calculation (see Table 1: “Control – Poor Sleepers (N=4)”, “Control – Good Sleepers (N=3)”, and “Sleep-Induced (N=8)”). We will be able to detect similar pM*hr differences as from the preliminary data between all groups and all A β isoforms with 13 participants in each group (effect size d range=1.17-1.57, $\alpha = 0.05$, Power $(1-\beta) = 0.8$), therefore this study is adequately powered with 15 participants in each group.

Alternative Approaches: We chose serial CSF collection via lumbar catheterization for the experimental approach because it provides the most detailed measures of A β kinetics and concentrations. An alternative approach could be to perform $^{13}\text{C}_6$ -leucine labeling with one lumbar puncture performed after the sleep period; differences in A β kinetics could be inferred by percent labeling of A β . However, with this approach the time relative to each participant's final awakening may be variable for each participant (e.g. 08:00 vs. 09:00) and does not easily account for different sleep start times. A larger sample size may also be required with this approach. Other potential problems for this study include participant recruitment and study completion. This study is intensive for participants. However, our preliminary study is similarly intensive and we have been able to achieve participant recruitment and completion goals. Screening participants by good and poor sleep efficiency may be more difficult than anticipated because participants will initially be referred from the community-based participant registry, Volunteers for Health, based on self-report and questionnaires. These measures may not correlate with the sleep efficiency found by actigraphy. If this occurs, we will need to screen more participants than

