Assignment to a study group: Participants with good sleep efficiency will not be randomized but will be placed in the “good sleep efficiency” group for Aim 1 and receive placebo. Participants with poor sleep efficiency will be randomized to receive their placebo (Aim 1) or suvorexant (Aim 2) at the research unit admission. The 45 participants in the poor sleep efficiency group will be randomized to receive placebo (15 participants) or suvorexant 10 or 20 mg (30 participants). 15 participants will receive 10 mg of suvorexant for two nights and 15 participants will receive 20 mg of suvorexant for two nights. In addition to being a FDA approved drug for the treatment of insomnia, suvorexant is also a drug with the same mechanism of action as was used in experiments to decrease A β with sleep in mice, therefore this will be a direct translation of this finding. FDA approved doses range from 5-20 mg. The drug’s mechanism of action is to block orexin-A and orexin-B receptors. The orexin neuropeptide acts in the brain to promote wakefulness. Through antagonism of this system, sleep is induced. In a phase IIb randomized, double-blind, placebo-controlled study of patients with primary insomnia, suvorexant 10 mg increased sleep efficiency from 65.1% at baseline to 82.9% at night 1 and 84.4% at one month. Placebo-treated subjects increased sleep efficiency from 65.9% at baseline to 76.8% at night 1 and 77.8% at one month [Ref. 48].

Collaborating sites: None

B. Sources of Materials

Specimens, records, or data: We will obtain the following from our participants (de-identified)

- Cerebrospinal fluid (CSF) specimens: Each participant regardless of study aim or group will have an indwelling lumbar catheter placed for the collection of CSF every 2 hours for 36 hours (hours 0, 2, 4, 6, 8, 10, 12, 14, 16, 18, 20, 22, 24, 26, 28, 30, 32, 34, 36). At each time point, 6 ml of CSF will be collected. At the end of the study an additional 2 ml of CSF (when available) will be sent to the lab to check for any signs of infection.

Therefore, a total of 116 ml of CSF will be collected from each participant over 36 hours. It is expected that the catheter will fail to draw CSF during the study for some participants. This will result in missing CSF samples and missing CSF safety labs.

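### The planned concentration tests make no explicit use of hour-0 CSF; a common hour-0 mean for the three randomised poor-sleep arms would be a cheap, optional gain in precision

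*Combined protocol and SAP*

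**What the plan says.** The Statistical Analysis and Power Calculation section sets the groups: "15 participants with good sleep efficiency will be treated with placebo (Aim 1") and "45 participants with poor sleep efficiency will be randomized to either placebo (N=15) (Aim 1) or suvorexant 10 mg (N=15) or suvorexant 20 mg (N=15"). The contrast for Aim 1 then concerns A-beta measures in "placebo-treated participants with poor sleep efficiency will be compared to placebo-treated participants with good sleep efficiency (Aim 1"). Aim 2 compares the same placebo poor sleepers with the suvorexant arms.

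That section plans repeated-measures ANOVA, or ANCOVA with covariates such as age. It tests average concentration over the sleep period by the main effect of group, and production by a group-by-time interaction. Other mixed models are left open. The hour-0 level is not named as a covariate, and no constraint on hour-0 means is mentioned. The sample size rests on a "calculation with two-tailed t-tests to detect a difference between two independent means (two groups"), applied to the AUC from 23:00 to 09:00.

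Under Assignment to a study group, "Participants with poor sleep efficiency will be randomized to receive their placebo (Aim 1) or suvorexant (Aim 2) at the research unit admission". Under Sources of Materials, "Each participant regardless of study aim or group will have an indwelling lumbar catheter placed for the collection of CSF every 2 hours", with hour 0 first on the list of draws.

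**The concern.** Randomisation gives the placebo, 10 mg and 20 mg arms the same expected hour-0 concentration, provided the draw precedes the first dose. The 30 suvorexant participants therefore carry information on where the placebo arm started relative to poor sleepers in general. If hour-0 and sleep-period levels are correlated, that information sharpens the placebo arm's sleep-period mean, and so both aims.

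The plan as written does not draw on it. Hour 0 falls at about 21:00, outside the powered window. In a group-by-time model with free means and complete data, each group's sleep-period mean comes from its own participants. The hour-0 values of the other 30 then add essentially nothing to good versus poor-placebo.

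At stake is precision in a trial with 15 per arm, whose protocol acknowledges that its power calculation rests on small preliminary numbers (groups of 3, 4 and 8). No bias is involved.

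**Working it through.** **Inputs from the documents.** 15 good sleepers; 45 poor sleepers randomised 15:15:15; two-sided alpha 0.05; target power 0.80; d from 1.17 to 1.57; 13 per group needed and 15 planned.

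**Assumed.** The correlation r between hour-0 level B and sleep-period level Y is taken as 0.3 to 0.9. Both have the same SD, s, in all groups, and hour 0 is drawn before dosing.

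**The plan's own figure.** A two-sample t-test (noncentral t) at d = 1.17 needs 13 per group, with power 0.816, so the stated figure reproduces. With 15 per group, power is 0.871 at d = 1.17 and 0.986 at d = 1.57.

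**Timing.** Aim 1 places t = 24 at 21:00 on Day 2, so t = 0 is about 21:00 on Day 1. The 23:00-09:00 window holds the samples from t = 2 to t = 12. Both nights are dosed, so in the suvorexant arms the only clearly usable pre-dose CSF is the single t = 0 sample. The label infusion starts at t = 0, so that sample holds no production or clearance information.

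**Aim 1, concentration level.** As planned, the variance of good versus poor-placebo is 2s²/15. With a common hour-0 mean, the poor-placebo estimate becomes its Y mean minus slope × (its B mean - B mean of all 45). Its variance is (s²/15) × [(1 - r²) + r²/3] = (s²/15)(1 - 2r²/3). The good sleepers keep their own hour-0 mean and contribute s²/15. The sum is (s²/15)(2 - 2r²/3), so the ratio to the planned variance is 1 - r²/3.

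**Aim 2, concentration level.** The mean of all 45 cancels between randomised arms. The variance is (2s²/15)(1 - r²), so the ratio is 1 - r².

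**Aim 1, change from hour 0.** With equal SDs, the squared correlation of Y - B with B is (1 - r)/2. Putting this in place of r² gives 1 - (1 - r)/6 = (5 + r)/6.

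**Power.** The noncentrality is 1.17/√(2/15) = 3.20, divided by the SE ratio, with 28 degrees of freedom.

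| r | Aim 1 level, variance ratio | SE ratio | Power at d = 1.17 | Aim 2 level, variance ratio | Aim 1 change, variance ratio |
|---|---|---|---|---|---|
| as planned | 1.00 | 1.00 | 87% | 1.00 | 1.00 |
| 0.3 | 0.97 | 0.985 | 88% | 0.91 | 0.88 |
| 0.5 | 0.92 | 0.957 | 90% | 0.75 | 0.92 |
| 0.7 | 0.84 | 0.915 | 92% | 0.51 | 0.95 |
| 0.9 | 0.73 | 0.854 | 95% | 0.19 | 0.98 |

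The d of 1.17 refers to a level (AUC), so no power figure is attached to the change column. Power is before any multiplicity correction.

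Simulation with an estimated slope gives Aim 1 level ratios within about 0.01 of the table and 0.52 for Aim 2 at r = 0.7. At r = 0 the loss from estimating the slope is under 1% of variance for Aim 1 and about 2% for Aim 2.

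**The case against.** The strongest reply is that nothing here is wrong. Good versus poor-placebo is the right contrast for Aim 1, 15 per group already exceeds 80% power at the smallest planned d, and the plan leaves mixed models open. All of that stands, and it is why the point is optional.

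Three limits on the gain also stand:

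- The correlation is not documented. At r = 0.3 the SE falls by only 1.5%.
- The plan introduces its outcomes as changes. On that reading, at r = 0.7 to 0.9, the Aim 1 variance falls by only 2% to 5%. The specific concentration test and the power basis are levels, so the larger figures fit those passages, but the text does not settle it.
- Production rate is called a main question, and hour 0 does not help it directly.

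A reader might infer more than the documents support:

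- *That the hour-0 samples are discarded.* No section says so. They are collected from everyone and may enter the repeated-measures models.
- *That Aim 1 should use all 45 poor sleepers.* The other 30 are on suvorexant throughout the outcome window on both nights. Hypothesis 2 expects the drug to lower A-beta, so pooling their sleep-period data would pull Aim 1 towards no difference. A 15 v 45 comparison is available only for the hour-0 level, which is a different question.
- *That sharing one placebo arm inflates error.* The two estimates have correlation 0.50, so both one-sided 2.5% tests reject together 0.46% of the time under the null, against 0.06% if independent. Each test keeps its own error rate, the sharing is stated openly, a multiplicity correction is promised, and no joint error rate is claimed.
- *That hour 0 is needed to escape a placebo response.* The Aim 2 text reports that "Placebo-treated subjects increased sleep efficiency from 65.9% at baseline to 76.8% at night 1 and 77.8% at one month". The night-1 rise of 10.9 points (76.8 - 65.9) is a before-after change in sleep efficiency in another trial's insomnia patients. It does not isolate a placebo response and says nothing about A-beta.

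**Conclusion.** The point holds as an optional, inexpensive improvement for concentration only. The planned tests do not specify use of a baseline that every participant is scheduled to give and that randomisation makes comparable across the three poor-sleep arms. For the concentration level, using it would cut the Aim 1 variance by 3% to 27% and the Aim 2 variance by 9% to 81% as r goes from 0.3 to 0.9. On the change reading, the Aim 1 cut is 12% down to 2% over the same range.

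These sizes rest on an assumed r, equal SDs and a pre-dose hour-0 draw. The documents do not support calling the planned contrast wrong, the sample discarded, or the type I error uncontrolled.

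**What to change.** In Statistical Analysis and Power Calculation, for concentration only:

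1. Fit one mixed model per isoform to all 60 participants, with hour 0 included as a response.
2. Give the three randomised poor-sleep arms a common hour-0 mean. Give the good-sleep group its own, because it is not randomised and a long-standing difference must be kept.
3. Take the Aim 1 contrast (good v poor-placebo) and the Aim 2 contrasts for sleep-period concentration from this model.
4. State whether the concentration outcome is the level or the change from hour 0.
5. State that hour 0 is drawn before the first dose, and confirm this from the sampling and dosing times. If it cannot be confirmed, omit the common mean.
6. Treat any hour-0 comparison of 15 good with 45 poor sleepers as descriptive at most, since it concerns the evening level.

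Leave the production and clearance analyses unchanged. The cost is a paragraph of plan wording and a few lines in the mixed-model software already named, with no new participants or samples. The downsides are slightly more modelling work and a negligible gain if r is low.
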